6.3.1.6 Adverse event outcomes

Adverse event outcomes will be judged on the following five levels

return to origin	evaluation criteria		
recovery	Adverse events have resolved or returned to normal.		
light	Adverse events have not fully recovered, but have largely disappeared or returned to almost		
	normal.		
Recovered but with sequelae	Adverse events have recovered to normal, but sequelae remain.		
unrecovered	Adverse events are ongoing.		
death	The patient died as a result of an adverse event.		
unknown	No information is available and outcome is unknown.		

6.3.2 Collection of adverse events

Adverse events will be collected at 1, 3, and 8 weeks after administration of the investigational drug. If an adverse event is observed in a subject during the clinical trial, the investigator (subinvestigator) will immediately take appropriate medical measures to ensure the subject's safety and inform the subject if treatment for the adverse event is necessary.

If an exacerbation of depressive symptoms is observed, a visit to the investigational site or a consultation with a psychiatrist (subinvestigator) should be conducted.

Adverse events shall be followed up until the subject recovers. However, if the outcome is unrecovered or minor at the end of the trial, follow-up is not required only when the event has stabilized and the investigator (subinvestigator) determines that follow-up is not required, with the reason clearly stated in the source documents.

6.3.3 Adverse event reporting and procedures

6.3.3.1 Serious adverse event reporting

If an adverse event occurs in a subject from the start of administration of the investigational drug until 8 weeks after the start of administration, and the investigator determines that the event is serious, the adverse event information will

639	be handled according to the following procedures.
640	Regardless of the causal relationship, the investigator shall report the event as soon as possible (within 24 hours) to the
641	head of the site and to the coordinating investigator in accordance with the "Procedures for Handling Safety Information"
642	The starting date of the reporting deadline shall be the date when the investigator becomes aware of the occurrence of
643	a serious adverse event.
644	(1) Notification by the investigator coordinating the clinical trial to the investigators at each site
645	The coordinating investigator shall review the contents of the adverse event report obtained from the investigator
646	and notify the relevant adverse event information to the investigators at each of the other sites.
647	(2) Consultation between the investigator and coordinating investigator
648	The investigator at each site checks the contents of the report obtained from the coordinating investigator, consult
649	with the coordinating investigator as necessary, and reports his/her opinion as the investigator (including the
650	necessity of reporting to the Minister of Health, Labor and Welfare) to the coordinating investigator.
651	(3) Report to the Minister of Health, Labor and Welfare
652	If the investigator determines that a report to the Minister of Health, Labour and Welfare is necessary, the
653	coordinating investigator shall prepare "Forms 7 and 8" and "Organizing Sheet" and report to the Pharmaceutical
654	and Medical Devices Agency (hereinafter referred to as the "Agency"). The coordinating physician shall report to the
655	Pharmaceuticals and Medical Devices Agency (hereinafter referred to as the "Agency"). In addition, the coordinating
656	physician shall provide information to Eisai Co.
657	(6) Report to the head of the medical institution
658	When a report is made to the Minister of Health, Labour and Welfare regarding a serious adverse event that occurred
659	at another medical institution, the investigator shall report the contents of "Forms 7 and 8" obtained from the
660	coordinating investigator to the head of the implementing medical institution as soon as possible.
661	(7) Actions to be taken when additional information is obtained
662	The investigator of the site where the adverse event occurred shall make an additional report to the head of the site
663	as soon as possible and to the coordinating investigator when additional information regarding the event is obtained
664	The same procedure shall be followed for reporting and notification of such additional information.
665	
666	6.3.3.2 Information provided by the investigator
667	The investigator who conducts the clinical trial himself/herself shall promptly inform the head of the site when he/she
668	obtains information on all serious and unpredictable adverse effects, etc., and information that may adversely affect the
669	safety of the subject, affect the conduct of the clinical trial, or change the approval of the investigational review committee
670	regarding the continuation of the clinical trial.
671	
672	6.3.4 drug overdose

In the event of an overdose of an investigational drug, whether intentional or negligent, the coordinating investigator

and the Clinical Trial Coordinating Office should be notified immediately. In case of overdose, the investigator will check

673

the safety of the subject and decide whether the investigational drug can be continued or not. The occurrence of overdosage and the safety of the subject will be described in the source documents. If a serious adverse event occurs due to overdosage, it should be reported as described in 6.3.3.1 Serious adverse events.

6.3.5 pregnancy

Detailed information will be collected on all pregnancies in female subjects and their male partners from the start of the investigational drug until 8 weeks after the start of treatment. If pregnancy is reported, the investigator will report it according to the same procedure as in 6.3.3.1 Report of Serious Adverse Events.

6.4 Other Evaluations

685 na

c: Performed only when the subject comes to the hospital

699

- 704 d: Blood tests at 3 weeks after the start of treatment and at 8 weeks after the start of treatment are optional and performed
- at the discretion of the patient and the investigator (subinvestigator).
- 706 e: Biomarker and pre-trial clinical examinations should be performed as an outpatient or during home visits prior to the
- 707 administration of the study drug if they cannot be performed during the pre-trial period (including cases where the pre-
- trial period was performed during the online medical examination).
- 709 f: Outcome symptom surveys shall be Chalder Fatigue Scale, HADS, IES-R, EQ-5D-5L, and PHQ-9.
- 710 G: The investigational drug will be taken for 3 weeks (21 days) regardless of the date of the patient's visit 3 weeks after
- 711 the start of administration.
- 712 h: The investigational drug will be collected only if it is discontinued during the period of administration of the
- 713 investigational drug.

- 715 7.2 Details of the test procedure for each Visit
- 716 7.2.1 remote medical examination
- 717 If consent is obtained while the subject is under COVID-19 isolation (including cases in which the subject is a
- 718 concentrated contact), it is possible to obtain consent remotely. Note, however, that if consent is obtained remotely, a
- 719 visit to the hospital or a clinic visit will be required for biomarker blood collection and clinical examination during the
- 720 preanalytic period. If the patient is unable to come to the hospital 1 week after the start of treatment, 3 weeks after the
- 721 start of treatment, or 8 weeks after the start of treatment, or if there are reasons why the patient is unable to come to
- 722 the hospital, the investigator (or collaborator) will conduct the items specified in "7.1Visit Schedule" by remote
- 723 consultation using online medical services.

724

- 725 7.2.2 home visitation (esp. of a patient)
- 726 If the items specified in "7.1Visit Schedule" are feasible at the discretion of the investigator (responsible party), the
- 727 home visit is permitted. However, when conducting home visits, procedures for home visits must be established at each
- 728 site and the procedures must be followed.

729

- 730 7.2.3 pre-observation period
- 731 The investigator obtains consent from the subject. Consent will be obtained in paper form or by eConsent at the
- discretion of the investigator, depending on the condition of the subject. The investigator will then confirm whether the
- subject is eligible for the study and include the subject in the clinical trial. The items to be conducted during the pre-
- observation period will follow "7.1Visit Schedule".

735

- 736 7.2.4 Duration of investigational drug administration
- 737 The duration of study drug administration is 3 weeks. During the study drug administration period, subjects will
- 738 receiveeither donepezil or placebo. The protocol for the dosing period will follow "7.1Visit Schedule".

740 7.2.5 time of discontinuance

741 Patients who discontinue during the study period will be followed up either in clinic or via online clinic to perform a Visit

742 at Discontinuation. For patients who discontinue the study drug during the study period and are unable to come to the

743 hospital, the investigational drug remaining at home will be returned to the medical institution under the direction of the

investigator (subinvestigator). In addition, when follow-up is conducted by telephone, the investigator will instruct the

subject to come to the hospital if necessary if an adverse event is observed in the subject.

745746

744

747 7.2.6 Duration of follow-up and completion of the clinical trial

748 Subjects who have completed the study drug administration period will be followed up at 3 weeks and 8 weeks after the

start of the study drug administration in principle in the clinic. If it is difficult to visit the clinic, online follow-up is

acceptable. The study will be terminated at the 8-week follow-up.

751752

749

- 8 Statistical Analysis and Sample Size
- 753 8.1 null hypothesis and alternative hypothesis

754 The null hypothesis: there is no difference in a priori primary outcome between donepezil and placebo groups for

755 patients with mild to moderate COVID-19 disease.

756

- 757 8.2 analysis plan
- The primary endpoints are compared using t-tests and regression models, while other outcomes and observables are
- 759 compared using t-tests, Wilcoxon tests, $\chi 2$ tests, and regression models.

760

- 761 8.2.1 Treatment of Interim Events
- In this study, the use of concomitant medications prohibited by the study protocol, treatment discontinuation, pregnancy,
- and death will be treated as intermediary events and considered in the analysis.

764

- 765 8.2.2 Primary Objective Analysis
- 766 8.2.2.1 Sensitivity Analysis
- Both intention—to—treat and per—protocol analyses will be performed.

768

- 769 8.2.2.2 subgroup analysis
- Subgroup analysis by age, gender, history, and severity of disease.

771

- 772 8.2.2.3 Additional Analysis
- Not planned at this time.

775 8.2.3 Analysis of secondary objectives

776 Secondary endpoints are compared using t-tests and regression models. Other outcomes and observations are

777 compared using t-tests, Wilcoxon tests, χ 2 tests, and regression models. Mixed effects models and generalized estimating

778 equations will be used for time series data.

779

- 780 8.2.4 Other Purpose Analysis
- 781 The outcome is defined as donepezil response, and multivariate regression models and Lasso regression are used to
- 782 search for characteristic biomarkers.

783

- 784 8.2.5 Interim Analysis
- No interim analysis will be performed in this trial.

786

- 787 8.3 Handling of Missing Data
- 788 Identify intermediate events or missing measurements, and for those that can be followed up, address the missing
- 789 measurements by referring to the hospital chart or by asking the patient. If missing data cannot be filled in, supplement as
- 790 necessary.

791

- 792 8.4 randomization
- 793 Block randomization will be employed in this trial.

794

- 795 8.5 Sample size setting
- 796 In a double-blind randomized controlled trial (n=200) with CFQ-11 as the outcome of COVID-19 by Rathi et al. the
- 797 mean CFQ-11 of patients in the placebo group on days 8, 11 and 14 of COVID-19 onset is 21.75, 20.55 and 19.91,
- 798 respectively, and therefore the patients participate CFQ-11 at timing, i.e., the baseline CFQ-11 value was set at 20
- 799 (Rathi A et al. Medicines (Basel) 2021;8(9)47). In this study, CFQ-11 values decreased from baseline to day and time in
- 800 both groups from day 0. The mean CFQ-11 value of 128 COVID-19 patients months after onset was 15.8±5.9 (Townsend
- $L\ \text{et al. PLOS ONE 2020;} 15(11): e0240784),\ \text{and this figure was similar in another outpatient study of } 458\ \text{patients}\ (\ \text{Stavem})$
- 802 K et al. Int J Environ Res Public Health. 2021;18(4):2030). Based on these studies, the mean CFQ-11 score after one
- 803 month in the non-treated group was set at 15 ± 5 and the amount of decline at 5, and the expected treatment effect was
- set at a 3-point reduction in minimal important difference from previous studies (Nordin Asa et al. BMC Med Res Methodol.
- 805 2016;16:62). Assuming a dropout rate of about 25%, we set α error = 0.5 and β error = 0.20. Based on these values, we
- set the number of patients to 120, 60 in each group.

- 808 [Sample size design (modified: February 12, 2023)
- 809 At the February 9, 2023 study group meeting, it was determined that the 8th group of COVID-19 was winding down, and
- as a result, it would be difficult to collect the above sample size by the scheduled time. As a result, it was determined that

it would be difficult to collect the above sample size by the scheduled date. Therefore, the sample size calculation was performed again due to the revised patient inclusion criteria. The revised inclusion criteria were changed from "within 21 days of disease onset" to "within 52 weeks of COVID-19 onset to randomization," so CFQ-11 scores obtained from previous publications at approximately one year after COVID-19 onset were used. A study in Ireland that followed patients hospitalized with COVID-19 for approximately one year showed a CFQ of 16.7 \pm 5.6 after a mean follow-up of 430 days (O'Brien K, et al. Respir Res. 2022 23(1):115), a Spanish population-based stdy study found a CFQ-11 of 8 \pm 3 after a mean of 36 weeks (Jimeno-Almazan A et al. Intern Emerg Med. 2022; 17(8):2199-2208). Also, in a German study, the CFQ-11 of 42 patients followed with severe fatigue after approximately one year was 21 \pm 5 (Kedor C. et al. Nat Commun. 2022;13(1):5104), and values varied among the patients studied. Considering the patient population used in previous sample size calculations, the CFQ of 15 \pm 5 at several months after onset and the CFQ-11 of 16.7 \pm 5.6 after an average of 430 days of follow-up in Ireland seem consistent. Therefore, we assumed a CFQ of 15 \pm 5 at one year after onset and set the minimal important difference to be a 3-point drop in the CFQ-11 score. Assuming a dropout rate of about 25%, we calculated α error = 0.5 and β error = 0.20, resulting in a total of 120 patients (60 in each group), unchanged from the sample size required for the original analysis.

- 9 Policies on obtaining consent, clinical trial records, data protection, and publication; clinical trial management organization
- 828 9.1 Approval of clinical trials, information to patients and obtaining consent
- This clinical trial will be initiated only after the Investigational Review Board (IRB) has reviewed and approved all required legal documents in accordance with GCP standards. This applies equally to conduct after the regulations have been amended.
 - Obtain consent from each patient prior to participation in the clinical trial. Consent should be obtained in writing (paper) or by electronic signature. When consent is obtained in paper form, a copy of the explanation document and signed consent form is provided to the patient. If consent is obtained electronically, it is performed remotely using eConsent, and the written explanation and electronically signed consent form are provided to the patient.
- The investigator must provide sufficient explanation to the patient using the explanatory document. Language that can be understood by the patient should be used, and technical terms and expressions should be avoided to the greatest extent possible.
 - The investigator must also give the patient sufficient time to consider participation in the study, and obtain the patient's free and voluntary consent after confirming that the patient understands the content of the consent form. The investigator signs the consent form (including electronic signature) in the same manner as the patient. If a collaborator provides supplementary explanations, the collaborator must also sign the consent form (including electronic signature).
- Re-consent must be obtained in the event of new significant findings regarding this clinical trial.

- 845 9.2 Data Quality Assurance
 - Data on all subjects in this clinical trial will be recorded on paper or electronic case report forms. The investigator is

responsible for verifying that the entries are accurate and correct by electronically signing the electronic case report form.

The investigator (sub)investigator should keep accurate records (source documents) to support the information provided in the electronic case report form.

Monitoring personnel shall conduct ongoing source document review to ensure that electronic case report data entered by authorized site personnel are accurate and verifiable from source documents, that the safety and rights of subjects are protected, and that the study is conducted in accordance with the study protocol (and other study-related documents) and all applicable regulatory requirements, The investigator confirms that the data in the electronic case report is accurate and verifiable from source documents, that the safety and rights of subjects are protected, and that the study is being

conducted in accordance with the protocol (and other clinical trial documents) and all applicable regulatory requirements.

9.3 record

858 9.3.1 original source

All source documents shallbe accurate, clear, unambiguous, unaltered, and available for inspection. The investigator (sub)investigator is responsible for ensuring that the accuracy, legibility, contemporaneity, originality, and pneumaticity of source documents are maintained, regardless of whether the data are written on paper or entered electronically. Original documents should not be obscured by the use of correction fluid or temporarily attached to documents (e.g., by the use of sticky notes). Copies of case report forms, etc. shall not be considered source documents.

Source documents are the original records from which raw data were first recorded. Source documents include hospital/clinic/general practitioner records, medical records, laboratory results, printed materials, pharmacy records, medical records, completed rating scales, etc. Original documents are stored in a secure location with restricted access. Source documents created by computer and stored electronically shall be printed for review by the monitoring staff if they are not accessible from the medical record, etc. and cannot be reviewed by the monitoring staff. The printed materials shall be signed and dated by the investigator(s) responsible for the study and kept as the source documents for the subject concerned. The source data shall also comply with all laws and regulations regarding the use of electronic records and electronic signatures via computer systems or other electronic systems.

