- 265 This is a phase 2, randomized, double-blind, investigator-initiated clinical trial (investigator-initiated clinical trial) of 266 donepezil in patients with mild to moderate COVID-19 with fatigue symptoms, ages 20 to <75 years, with symptoms of 267 COVID-19, and within 52 weeks of onset of symptoms. patients aged 20 to less than 75 years with COVID-19 symptoms 268 and a Chalder Fatigue Score-11 dichotomous score of ≥4 within 52 weeks of onset of symptoms. Participation in the study 269 will last for 8 weeks, and subjects who consent and are eligible will receive standard treatment for COVID-19 (or none if 270 no treatment is needed) and will be randomized in a 1:1 ratio to either the donepezil or placebo group. The subjects will 271 then receive either donepezil or placebo for 3 weeks in a double-blind fashion, with follow-up assessments at 3 weeks and
- 272 8 weeks after the start of the study drug. The number of subjects will be 60 in each group, for a total of 120 subjects.
- 273

The test drug will be donepezil (Aricept) powder purchased from the market under the technical guidance of Eisai Inc.

274 and the control drug will be lactose powder as placebo.

275 276

- 3.2 Considerations for Clinical Trial Design
- 277 The purpose of this trial is to evaluate the efficacy of donepezil in patients with COVID-19 sequelae.
- 278 After COVID-19 positivity is confirmed by antigen or PCR and eligibility is confirmed with standard therapy, patients will
- 279 be started on donepezil or placebo. Patients will be started on a low dose (3 mg donepezil) for the first week of treatment
- 280 to determine if any gastrointestinal adverse events occur. If no adverse events attributable to donepezil are observed, the
- 281 dose is increased (5 mg donepezil) for 2 weeks. The design of this study is in accordance with the donepezil package insert,
- 282 and we believe that there are no safety issues for patients. Based on the results of basic research, it is expected that
- 283 sufficient efficacy can be determined during the post-dose escalation period. Outcome symptom evaluation will also be
- 284 conducted after 8 weeks of investigational use for long-term confirmation as a post-dose evaluation.
- 285 Based on the above, we believe that this is an appropriate design for this clinical trial.

286

- 287 Study Population and Discontinuation Criteria 4
- 288 4.1 target disease
- 289 Patients with mild to moderate COVID-19 with malaise symptoms.

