
the most appropriate description for each of the five items. The subject records his/her self-assessment of his/her health

status by means of the "best imaginable health status" and "worst imaginable health status. This VAS can be used as a quantitative value of health status reflecting the subject's own judgment.

476477

475

- 478 6.1.5 Patient Health Questionnaire-9 (PHQ-9)
- The PHQ-9 is a questionnaire designed to screen for the presence and severity of depression. It consists of nine items
- on "depressed mood" and "loss of interest" in the last two weeks. Mood" and "Decrease or loss of interest" for the last 2
- 481 weeks. Each item is rated on a four-point scale: not at all, a few days, more than half of the time, and almost every day.
- 482 If even one of the nine items applies to the patient, the effect on work, housework, and interpersonal relationships is rated
- 483 on a four-point scale: not at all difficult, somewhat difficult, difficult, and extremely difficult.
- Instruct the subjects to check the checkboxes for the applicable items.

485

- 486 6.1.6 Amount of activity, duration of activity
- 487 A Yamasa pedometer (model number: TM-510) will be used to measure the number of steps taken. The device will be
- 488 worn daily from the start of treatment until 3 weeks after the start of treatment. The device should be worn daily from the
- time the patient wakes up to the time the patient goes to bed, if possible.
- 490 The next day, the number of steps taken is recorded on the medication logbook for the previous day. Using an electronic
- 491 medication logbook (Viedoc Me), the subject will take a picture of the step count screen and upload the image to the
- 492 electronic medication logbook.
- 493 Procedures for electronic medication logbooks are specified separately.

494

- 495 6.1.7 Biomarker Evaluation in Blood Testing
- Biomarkers will be performed during the preobservation period.
- 497 Biomarkers will be collected by SRL Corporation. Procedures for blood collection and pickup will be determined separately.

498

- 499 6.2 Safety Assessment
- 500 6.2.1 Subject Background
- During the preanalytic period, the following background information will be checked: sex, age, date of birth, date of onset
- 502 of COVID-19, complications and history, and concomitant medications/adjunctive therapies. However, the date of birth
- $\,\,503\,\,$ will be entered only in the Web registration system.

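### Entry was widened from 21 days to 52 weeks after onset with no lower limit, but neither the primary t-test nor the fixed subgroup list uses time since onset; this costs precision and interpretability, not validity

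*Protocol*

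**What the plan says.** **Purpose.** Protocol 3.2: "The purpose of this trial is to evaluate the efficacy of donepezil in patients with COVID-19 sequelae".

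**Entry.** Inclusion criterion 4 (section 4.2) requires randomisation within 52 weeks of onset and sets no minimum time since onset. Section 8.5 (modification of 12 February 2023) records that the limit had been 21 days and is now "within 52 weeks of COVID-19 onset to randomization". Acute entry is still foreseen. Section 7.2.1 provides for remote consent: "If consent is obtained while the subject is under COVID-19 isolation".

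**Expected course.** The first calculation in 8.5 takes a baseline of 20, and the score after one "month in the non-treated group was set at 15 ± 5 and the amount of decline at 5". The revised calculation takes 15 ± 5 at one year and gives no figure for untreated change.

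**Analysis.** Section 8.2 compares the primary endpoint by t-tests and regression models and names no covariate. Section 8.2.2.2 lists: "Subgroup analysis by age, gender, history, and severity of disease". Section 8.2.2.3 plans no additional analysis. Section 8.4 says only that block randomisation is used.

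**Data.** Section 6.2.1: "During the preanalytic period, the following background information will be checked: sex, age, date of birth, date of onset" of COVID-19.

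**The concern.** The amendment changed one patient characteristic, time since onset, by a wide margin. The sample size was reworked in response, but the list of analyses does not use that characteristic. Anyone enrolled under the old rule was within 21 days of onset. Patients enrolled later may be anywhere from a few days to a year out.

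The protocol's own planning figures say these patients behave differently: a 5-point untreated fall in about a month for early cases, and a settled level of about 15 for late ones. If so, spontaneous recovery in the early patients adds between-patient variation to the change score, and an unadjusted t-test leaves that variation in the error term.

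Interpretation also suffers. The trial seeks proof of concept in sequelae. A single pooled estimate, with no planned look by time since onset, cannot indicate whether an effect is seen in long-standing cases, in recent ones, or in both.

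**Working it through.** **Inputs from Protocol 8.5.** Difference 3 points; SD 5; power 80%; dropout 25%; and a total that the revision describes as "resulting in a total of 120 patients (60 in each group), unchanged from the sample size required for the original analysis". Alpha is printed as 0.5 ("Assuming a dropout rate of about 25%, we set α error = 0.5 and β error = 0.20"). It is taken here as 0.05 two-sided, because that value reproduces the stated total.

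**Step 1: reproduce the plan's figure.** Standardised effect = 3/5 = 0.6. The two-sample t-test at 0.05 and 80% power needs 44.6, so 45 per arm. Then 45/0.75 = 60 per arm, or 120 in total, which matches. Power at 45 evaluable per arm is 80.4%.

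**Step 2: effect of mixing on the change score.** Let p be the share of early patients and g the gap in mean untreated change between early and late patients. With SD 5 within each stratum and a common 3-point treatment effect:

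SD² = 25 + g²·p(1 − p)

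The protocol does not give p or g for the enrolled mix, nor the SD of the change score. All three are assumptions. The value g = 5 comes from the 5-point decline in 8.5, set against no decline in late patients.

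| g | p | SD² | SD | t-test power, 45 per arm |
|---|---|---|---|---|
| 0 | any | 25.00 | 5.00 | 80.4% |
| 3 | 0.2 | 26.44 | 5.14 | 78.1% |
| 3 | 0.5 | 27.25 | 5.22 | 76.9% |
| 5 | 0.2 | 29.00 | 5.39 | 74.3% |
| 5 | 0.3 | 30.25 | 5.50 | 72.5% |
| 5 | 0.5 | 31.25 | 5.59 | 71.1% |

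**Step 3: what adjustment recovers.** With stratum in the model, the residual SD returns to about 5 and power to about 80%, provided the 3-point effect is the same in both strata. Adjustment does not recover power lost because the effect is smaller in early patients. With an assumed 1.5 points in early and 3 in late patients, residual SD 5 and p = 0.25, the average effect is 0.75 × 3 + 0.25 × 1.5 = 2.625 and power is about 70% (normal approximation). With p = 0.5 the average is 2.25 and power about 57%.

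**Step 4: what a subgroup can show.** Late patients number 36 per arm if p = 0.2 and 22.5 if p = 0.5. Power for 3 points in that subset alone is about 72% and 52% (normal approximation, SD 5). The standard error of the interaction is √(50/n_late + 50/n_early): √(50/36 + 50/9) = 2.64 for p = 0.2 and √(50/22.5 + 50/22.5) = 2.11 for p = 0.5. Power to detect even a full 3-point difference in effect is about 21% and 30%.

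**The case against.** **The SD of 5 is the SD of a score level, not of a change.** This stands. On the protocol's figures early patients go from 20 to 15, and late patients sit at 15. If the late patients do not move, the two groups have the same mean afterwards, and mixing adds nothing to the spread of the post-treatment level. The loss in Step 2 concerns the change score, whose SD the protocol never gives. It illustrates a possible cost and does not show that the trial is underpowered.

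**Covariates and strata may be in the SAP.** This stands in part. The protocol names no covariate, and leaving that detail to the SAP is ordinary, as is leaving stratification detail there. But the protocol itself fixes a t-test among the primary methods and fixes a subgroup list, and neither uses time since onset.

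**The population is also described more broadly.** Sections 4.1 and 8.1 refer to mild to moderate COVID-19, and a pooled 0–52 week comparison does answer that null hypothesis. This is a good reason to keep the pooled comparison primary. It does not remove the sequelae purpose in 3.2.

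**Stronger readings that are not supported.** A reader might infer that pooling biases the comparison. It does not: imbalance in the early share under randomisation is chance, and the test stays valid. A one-SD imbalance would shift the difference by 5·√(2p(1 − p)/45), or 0.42 to 0.53 points for p = 0.2 to 0.5. That is the extra variance of Step 2 expressed another way, not a second harm. A reader might also want the patients beyond 21 days treated as the real sequelae result. Twenty-one days is a former recruitment limit; section 1.1 says the definition of the disease is not established; and Step 4 shows how little power that subset has.

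**Conclusion.** The point holds as one of precision and interpretation. Entry was widened with no lower limit, the protocol's own figures make time since onset a likely prognostic factor for the primary change score, and neither the t-test nor the subgroup list uses it, although the data will be in hand.

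The size is conditional. With a within-stratum change-score SD of 5, a 5-point gap in untreated change and 20–50% early patients, unadjusted power is about 71–74% against 80%. With a 3-point gap the loss is 2 to 3.5 percentage points, and with no gap it is nil. These figures use the scoring on which 8.5 rests. Section 6.1.1 adopts binary scoring, with a maximum of 11, and they do not carry over to that scale. The documents do not support a claim that power has in fact fallen or that the comparison is biased.

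**What to change.** - **Section 8.2.** Make the primary comparison a regression of the Chalder score at 3 weeks (or its change) on treatment, adjusted for baseline score and time since onset. Time since onset can be continuous or split at ≤21 versus >21 days. The former entry limit is a convenient cut-point because it does not come from the data.
- **Section 8.2.2.2.** Add time since onset as a pre-specified subgroup. Report the treatment-by-time interaction with its confidence interval, and label it exploratory because its power is low.
- **Keep the pooled randomised comparison as primary**, and do not present the subset beyond 21 days as the definitive result for sequelae.

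The cost is one degree of freedom for time since onset and one more subgroup to report. No new data are needed. The change should be made before unblinding.
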